#### Post-Treatment Follow-up:

The intent is to obtain at least 3 months of follow-up on each subject after cessation of pegloticase infusions. If the subject ends treatment early but remains in the study and the 3- month Post Treatment Follow-up Visit occurs prior to Week 24, the 3-month Post Treatment Follow-up Visit will be adjusted accordingly based on the timing of the last treatment.

#### 9.3.3.2 Removal of Subjects From Study

In addition to completion of therapy and designated study visits through Week 24, the reason for discontinuation from the study should be recorded on the eCRF using 1 of the following categories:

- Lost to Follow-up: The subject does not return to the clinic for scheduled assessments, and does not respond to the site's attempts to contact the subject;
- Withdrawal by subject: The subject withdraws from the study. The clinical site should attempt to determine the underlying reason for the withdrawal and document it on the eCRF (i.e., voluntary withdraw, relocation, lack of transportation, etc.). The underlying reason should be specified;
- Study Terminated by Sponsor: The Sponsor, IRB, or regulatory agency terminates the study; and
- Death

#### 9.3.4 Replacement Policy

##### 9.3.4.1 Subjects

In general, subjects that prematurely discontinue from the study for any reason will not be replaced. An exception may be made for subjects who are unevaluable due to the impact of the COVID-19 pandemic and associated restrictions on movement and work. Subjects unable to receive treatment or be evaluated due to restrictions during the COVID-19 pandemic may be replaced, at the discretion of

the sponsor. This may result in more subjects than originally planned being enrolled into the study to allow for the originally planned number to be evaluable for the primary efficacy analysis.

#### 9.3.4.2 Centers

A center may be closed and/or replaced for the following administrative reasons:

- Excessively slow recruitment; or
- Poor protocol adherence.

#### 9.3.4.3 Screen Failures

Subjects who do not meet all of the eligibility criteria or withdraw consent between Screening and Day 1 will be considered screen failures. Screen failures may be allowed to rescreen for the study if both the Investigator and Sponsor are in agreement regarding rescreening and if the Investigator determines that they can satisfy all of the eligibility criteria.

Subjects who fail screening but consented to the optional blood draw for biomarker analysis will be requested to return to the site 24 weeks +/- 4 weeks for a second blood sample. Adverse events, concomitant medications, blood samples for hematology and clinical chemistry and vital signs will also be collected as an unscheduled visit at that time.

### 9.4 Treatments

#### 9.4.1 Treatments Administered

Starting at the Day 1 visit, subjects will receive pegloticase at a dose of 8 mg administered IV every 2 weeks for a total of 12 infusions from Day 1 through the Week 22 Visit.

After the Week 24 Visit, subjects should resume regular care for gout per the judgment of the treating physician, including resumption of ULT upon pegloticase discontinuation, if appropriate. Subjects will have a 3-month Follow-up visit to assess clinical status, including sUA levels.

##### 9.4.1.1 Gout Flare Prophylaxis

It is required that before a subject begins the treatment period, he or she has been taking protocol defined standard gout flare prophylaxis (i.e., colchicine initial dose 0.3-0.6 mg/day if tolerated and low-dose prednisone  $\leq$  10 mg/day); for subjects already taking low dose corticosteroids, colchicine 0.3-0.6 mg/day should be added. In subjects with eGFR  $\leq$  30 mL/min/1.73m^2, the dose of colchicine should not be more than 0.3 mg/day. In subjects taking cyclosporine, only low dose prednisone (and not colchicine) should be used for  $\geq$  1 week before the first infusion.

Gout flare prophylaxis should continue for the duration of the 24-week treatment period. Subjects should be monitored closely for symptoms of colchicine excess during the study. Reductions in dose, dose frequency or discontinuation of colchicine are permitted if not tolerated.

Prescriptions are to be filled at a local pharmacy, as needed. At study visits, the subject will be asked a Yes/No question whether gout flare prophylaxis was taken per protocol.

#### 9.4.1.2 Infusion Reaction Prophylaxis

Since IRs can occur with pegloticase, all subjects will receive IR prophylaxis prior to each infusion, consisting of an antihistamine, acetaminophen, and a corticosteroid. To standardize this regimen, subjects will receive fexofenadine (60 or 180 mg orally) the day before each infusion; fexofenadine (60 or 180 mg orally) and acetaminophen (1000 mg orally) the morning of each infusion. In addition, methylprednisolone (125 mg IV from Day 1 to Week 10 and 80 mg IV from Week 12 until the end of treatment) is recommended to be administered over an infusion duration between 10 and 30 minutes, immediately prior to each pegloticase infusion.

Alternate IV corticosteroid regimen may be substituted for methylprednisolone at the discretion of the Investigator. The dose of fexofenadine should be 60 mg orally in subjects with decreased renal function and 180 mg orally in subjects with normal renal function (eGFR

>90 mL/min/1.73m^2). Substitution of the corticosteroid is not allowed. The name, dose, route, date, and time of administration of each prophylactic medication will be recorded in the medical record and in the eCRF. The methylprednisolone used for IR prophylaxis will be supplied by the site. Other IR medications administered prior to each infusion may also be supplied by the site.

Prescriptions are to be filled at a local pharmacy, as needed. At study visits, the subject will be asked a Yes/No question whether IR prophylaxis was taken per protocol.

As a precaution, emergency equipment will be readily available to treat a possible hypersensitivity reaction, and will include drugs that would be used to treat an anaphylactic reaction. Personnel trained in managing IRs and in the use of the emergency equipment will be readily available during and for 1 hour after the infusion. As IRs can occur after the completion of the infusion, subjects will be observed for 1 hour post-infusion.

#### 9.4.2 Identity of Investigational Products

##### 9.4.2.1 Pegloticase

Pegloticase is a clear, colorless, sterile solution in phosphate-buffered saline (PBS) intended for IV infusion after dilution. Each mL of pegloticase contains 8 mg of uricase protein conjugated to 24 mg of 10 kDa monomethoxypoly(ethylene glycol). Excipients include disodium hydrogen phosphate dihydrate, sodium chloride, sodium dihydrogen phosphate dihydrate, and water for injection.

#### 9.4.3 Labeling

Pegloticase is commercially available in the United States as KRYSTEXXA and will be supplied by PCI Pharma Services packaged in sterile, single-use 2-mL glass vials with a Teflon®-coated (latex-free) rubber injection stopper to deliver pegloticase as 8 mg of uricase protein in 1 mL volume. An ancillary label will be fixed to the vial and carton that identifies the study, allows subject information to be entered, and contains the investigational use caution statement according to the FDA Title 21 CFR Part 312 requirements. Each vial label will have a unique number.

#### **9.4.4 Storage**

Before preparation for use, pegloticase will be stored in the carton, maintained under refrigeration between 2°C and 8°C (36°F and 46°F), protected from light, and will not be shaken or frozen. Pegloticase diluted in infusion bags is stable for 4 hours at 2°C to 8°C (36°F to 46°F) and for 4 hours at room temperature (20°C to 25°C, 68°F to 77°F).

#### **9.4.5 Drug Accountability**

Clinical supplies will be dispensed only in accordance with the protocol. Accurate records of the clinical supplies received, the amount dispensed for each subject, and the amount remaining at the conclusion of the study will be maintained.

Investigational clinical supplies will be received by a designated person at the study site, handled and stored safely and properly, and kept in a secured location to which only the Investigator and designated assistants have access.

Please reference the Study Pharmacy Manual for more detailed information on pegloticase packaging, labeling, storage, and destruction.

#### **9.4.6 Study Drug Administration and Timing of Dose for each Subject**

##### **9.4.6.1 Description of Clinical Supplies**

██████████ will supply pegloticase to clinical sites. Ancillary supplies for dosing will be provided by the study site (i.e., infusion bags containing saline, syringes, needles, alcohol swabs, gauze pads, bandages, and biohazard containers for safe storage of used needles and syringes).

##### **9.4.6.2 Determination of Dose Volume**

Pegloticase will be administered as an admixture of 8 mg in 250 mL of 0.45% or 0.9% Sodium Chloride Injection, United States Pharmacopeia (USP) for IV infusion.

In the event of an IR, the infusion should be slowed, or stopped, and restarted at a slower rate at the discretion of the Investigator. Infusions subsequent to an IR in an individual subject may be given in a larger volume of diluent, not to exceed 500 mL. In this case, the infusion duration will also be extended to a minimum of 3 hours.

##### **9.4.6.3 Details Concerning Timing and Dose Administration**

###### **9.4.6.3.1 Preparation and Administration**

###### **9.4.6.3.1.1 Preparation**

Vials of pegloticase will be visually inspected for particulate matter and discoloration before administration, whenever solution and container permit. Vials will not be used if either is present. Using appropriate aseptic technique, 1 mL of pegloticase will be withdrawn from the vial into a sterile syringe. Any unused portion of product remaining in the vial will be discarded. Syringe contents will be injected into a single 250 mL bag of 0.45% or 0.9% Sodium Chloride Injection, USP for IV infusion and will not be mixed or diluted with other drugs. The infusion bag containing the dilute pegloticase solution will be inverted a number of times to ensure thorough mixing but will not be

shaken. In accordance with good pharmacy practice, gloves will be worn during preparation of the dose.

The pegloticase infusion must be started within 4 hours of dilution. Before administration, the diluted solution of pegloticase will be allowed to reach room temperature. Pegloticase must never be subjected to artificial heating.

#### **9.4.6.3.1.2 Dose and Administration Pegloticase**

All subjects will receive pegloticase at the same dose of 8 mg administered IV every 2 weeks for a total of 12 infusions from Day 1 through the Week 22 Visit. Subjects will not be fasting on the day of infusion and will be encouraged to have a snack or normal meal before or after the infusion. Pre-infusion sUA results must be reported by the local or central laboratory prior to pegloticase infusion (see Section 9.5.1.1).

Standardized IR prophylaxis consisting of pre-treatment with antihistamines, acetaminophen, and corticosteroids will accompany each infusion (see Section 9.4.1.2). The drug name, dose, and timing of these prophylactic medications will be recorded.

Pegloticase will be administered as an admixture of 8 mg in 250 mL of 0.45% or 0.9% Sodium Chloride Injection, USP for IV infusion by gravity feed or infusion pump. Pegloticase will not be administered as an IV push or bolus.

In a patent IV site, the pegloticase preparation will be infused over a period of no less than 120 minutes while the subject is under close observation for any signs of distress. No in-line

filter is required; however, if an in-line filter is used, it should be 0.2 µm or larger. At the end of the infusion, the IV line will be flushed with 10 mL of normal saline to ensure the full dose is administered. The date and times of infusion start and stop (inclusive of the IV flush) will be recorded.

#### **9.4.6.3.2 Dose Modifications, Interruptions, and Delays**

##### **9.4.6.3.2.1 Pegloticase Modifications**

Infusion of pegloticase will be immediately interrupted if the subject experiences any significant IR such as respiratory distress, agitation, chest or back pain, urticaria, or another clinically significant event occurring during infusion. If the AE meets the definition of an SAE for IR, the infusion should not be restarted unless the site Investigator determines it is safe to resume the infusion. If the AE does not meet the definition of an SAE for IR, the site Investigator may make the decision to re-start the infusion depending upon the nature and severity of the AE.

Infusions subsequent to an IR in an individual subject may be given in a larger volume of diluent, not to exceed 500 mL. In this case, the infusion duration will also be extended to a minimum of 3 hours. The total volume and duration of infusion will be captured in the medical record and eCRF.

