#### 9.4.6.3.2.3 Infusion Reaction Treatment

Subjects must be monitored closely for signs and symptoms of IRs. In the event of an IR, the infusion should be slowed, or stopped, and restarted at a slower rate at the discretion of the Investigator. If a serious IR occurs, the infusion should be discontinued and treatment should be provided, as needed.

If a subject experiences an AE suspected to be an IR:

- A physical examination will be performed to capture medically relevant details, including, but not limited to, a thorough dermatologic examination for detection of erythema, urticaria (hives), or peri-oral or lingual edema; a chest examination for breath sounds, stridor or wheezing; and a cardiac examination with attention to the possibility of an irregular heartbeat;
- Vital signs (sitting or supine blood pressure, heart rate, respiratory rate, and body temperature) will be captured at least every 30 minutes until the resolution or stabilization of the AE;
- 12-lead ECG will be performed;
- A serum sample will be collected in a serum-separating tube at that time or at the subsequent visit. The sample will be centrifuged, frozen at -20°C or colder, and stored for the batch shipment to a Horizon designated laboratory for evaluation of pegloticase antibodies at a future date.

If, in the Investigator's opinion, the subject is experiencing an anaphylactic reaction (see Section 9.5.4.1.1.5), pegloticase should be immediately discontinued. Any incidence of anaphylaxis should be reported as an SAE.

The Investigator may administer any medically indicated pharmacologic agent or procedure intended to relieve symptoms (CAUTION: no other drugs can be mixed in the pegloticase infusion bag). Signs

and symptoms of the AE and drugs given for treatment are to be recorded in the medical record and in the eCRF.

After the first incidence of an IR that does not meet the criteria of anaphylaxis (see Section 9.5.4.1.1.5) or does not meet serious criteria, the Investigator may elect to initiate the next infusion at a slower rate. All changes to infusion rate or dilution, and drugs given for prophylaxis or treatment, are to be recorded in the medical record and in the eCRF.

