### **Infusion Reaction**

An IR will be defined as any infusion-related AE or cluster of temporally-related AEs, not attributable to another cause, which occur during the pegloticase infusion and for up to 2 hours post-infusion. Other AEs that occur outside of the 2-hour window following the infusion may also be categorized as an IR at the PI’s discretion. Signs and symptoms of the IR and treatments administered will be documented in the medical record and in the eCRF, and will be adjudicated.

Examples of AEs not considered possible IRs include, but are not limited to: laboratory abnormalities that are unlikely to have occurred during or within 2 hours following the infusion (e.g., anemia), gout flares, most infectious diseases, or the recurrence or worsening of a known chronic medical problem identified in the subject’s medical history.

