3. Reduced blood pressure after exposure to known allergen for that subject (minutes to several hours): systolic blood pressure  $<90$  mmHg or  $>30\%$  decrease from that subject's baseline.

The signs and symptoms associated with each event are entered on the eCRF and will be coded to the MedDRA dictionary.

Summaries of IRs and anaphylaxis will group events by 3 categories:

- Anaphylaxis
- Infusion reactions including anaphylaxis
- Infusion reactions excluding anaphylaxis

Both the investigator-reported and adjudicated events and the associated signs and symptoms, will be summarized separately by SOC, PT, severity, and the time relative to the most recent pegloticase infusion for each category above.

Time relative to the most recent pegloticase infusion will be categorized as: during infusion,  $\leq 2$  hours after infusion,  $> 2$  hours to 24 hours after infusion, and  $> 24$  hours after infusion. If the time of the infusion reaction or anaphylaxis is missing, the category will be assigned as "Missing".

This document is confidential.

Serious events and the associated symptoms will be summarized by SOC and PT for each category.

The number of events per subject, the number of events and serious events per infusion, and the number of subjects with the first event by infusion number will be summarized as well for each category. IRs (including anaphylaxis) that occur on the same date will be considered one event.

Time to first infusion reaction or anaphylaxis (Kaplan-Meier analysis) will be plotted. Time to first infusion reaction or anaphylaxis for subjects who experience infusion reaction or anaphylaxis (continuous variable descriptive stats) will be summarized. Summaries of events will be tabulated only if 5 or more subjects have either an event adjudicated as an IR or anaphylaxis or any events in the database identified as IRs or anaphylaxis.

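### Protocol sections 9.4.6.3.2.1 and 9.4.6.3.2.3 disagree on whether an infusion may be resumed after a serious infusion reaction, and the resumption clause has no carve-out for anaphylaxis

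*Protocol*

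**What the plan says.** Three Protocol sections instruct the site on what to do with a running infusion when an IR occurs.

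- **9.4.6.2 (Determination of Dose Volume)** gives a rule for any IR: "In the event of an IR, the infusion should be slowed, or stopped, and restarted at a slower rate at the discretion of the Investigator". It does not distinguish serious from non-serious reactions.
- **9.4.6.3.2.1 (Pegloticase Modifications)** requires immediate interruption for a significant IR and then addresses seriousness. For an IR that qualifies as an SAE, "the infusion should not be restarted unless the site Investigator determines it is safe to resume the infusion". For a non-serious event the restart is left to the Investigator.
- **9.4.6.3.2.3 (Infusion Reaction Treatment)** repeats the general sentence from 9.4.6.2 and continues: "If a serious IR occurs, the infusion should be discontinued and treatment should be provided, as needed". Where, in the Investigator's opinion, "the subject is experiencing an anaphylactic reaction (see Section 9.5.4.1.1.5), pegloticase should be immediately discontinued". The section also states: "Any incidence of anaphylaxis should be reported as an SAE".

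The definitions that decide which events these rules reach are in Protocol 9.5.4.1.1.5: "An IR will be defined as any infusion-related AE or cluster of temporally-related AEs, not attributable to another cause, which occur during the pegloticase infusion", with the window running on to 2 hours after the infusion. That definition does not exclude anaphylaxis. SAP 12.3.3.1 likewise has a summary category named "Infusion reactions including anaphylaxis".

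**The concern.** A site facing a serious IR during an infusion finds two instructions for the same event. One lets the Investigator resume if satisfied that it is safe. The other ends the infusion and mentions no resumption. Neither refers to the other, and the general sentence in 9.4.6.2 could be read as a third answer.

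What is at stake is the consistent handling of a safety event. IRs and anaphylaxis are both named adverse events of special interest, and reducing IR risk is part of the study's rationale. The conflict is one of instruction to sites. It is not an error in a calculation.

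**Working it through.** No figure in the plan depends on this point, so the check is mainly a comparison of text.

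**Step 1. Serious IR that is not anaphylaxis.**

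| Section | Instruction | Resumption of that infusion |
|---|---|---|
| 9.4.6.2 | Slow, or stop and restart, at discretion | Allowed; seriousness not mentioned |
| 9.4.6.3.2.1 | No restart unless judged safe | Allowed on a condition |
| 9.4.6.3.2.3 | Discontinue and treat | No route stated |

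The last two rows give different answers for one event. Within 9.4.6.3.2.3 the sentence on IRs in general speaks of stopping and restarting. The next sentence, on serious IRs, changes the verb and drops the restart. That contrast tells against reading the second sentence as a temporary stop.

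**Step 2. Anaphylaxis.** Anaphylaxis arising during an infusion fits the IR definition, the SAP counts it among IRs, and it is always reported as an SAE. Taken alone, the SAE clause of 9.4.6.3.2.1 therefore reaches it. That section contains no exclusion and no pointer to the anaphylaxis sentence in 9.4.6.3.2.3.

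**Step 3. Related wording.** The phrase in 9.4.6.3.2.1 about an SAE for IR has no definition of its own; only the general SAE definition in 9.5.4.1.1.2 exists. The last paragraph of 9.4.6.3.2.3, on slowing the next infusion, applies to a first IR that fails the anaphylaxis criteria *or* fails the serious criteria. With that conjunction, a serious but non-anaphylactic IR also qualifies, so the handling of the following infusion is unclear too.

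**Step 4. Size.** Inputs are from Protocol 7.1.2, with n = 20 from 9.6.9. Expected subjects = n × rate.

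- Any-severity IR, Phase 3, 8 mg every 2 weeks: 22/85 = 25.9%, which reproduces the stated 26%. 20 × 0.26 = 5.2.
- Any-severity IR, post hoc, had the stopping rule applied: 20 × 0.08 = 1.6.
- Anaphylaxis, post hoc, pooled over Phase 2 and Phase 3: 20 × 0.065 = 1.3.

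The conflict concerns serious IRs only, and resumption arises only for events during the infusion. The first two results are thus upper bounds on the number affected, if those rates carry over. The readable text gives neither the serious share nor the split between during and after infusion.

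**The case against.** The strongest reply is that the sections can be read together. Both start from not continuing after a serious IR. Section 9.4.6.3.2.3 refers to the infusion for a serious IR but to pegloticase for anaphylaxis, which suggests that the former concerns only that session. Section 9.4.6.3.2.1 could then be its exception. The distinction between session and drug is fair, and it narrows the point to resuming one infusion. The exception is not written anywhere, however, and neither section refers to the other, so the ambiguity remains.

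Four stronger readings may tempt a reader, and the documents do not support them.

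- **That the protocol permits a restart after anaphylaxis.** This needs 9.4.6.3.2.1 read in isolation. Section 9.4.6.3.2.3 deals with anaphylaxis specifically and requires immediate discontinuation, and 9.3.3.1 gives anaphylactic reaction as an example of an adverse event leading to discontinuation of therapy. What remains is a missing carve-out or cross-reference.
- **That interrupting and slowing contradict each other.** Stopping for a significant IR satisfies all three sections.
- **That about 2 to 5 of 20 subjects would meet the conflict.** Those numbers count IRs of any seriousness. For non-serious IRs all three sections leave a restart to the Investigator.
- **That responder status is affected.** SAP 10.2 uses uric acid results from visits without an infusion, except for subjects who meet the stopping rule. Protocol 9.6.5.1 makes withdrawal from treatment for other reasons a non-response only where the planned values are not collected.

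Nor does either serious-IR sentence set a rule on permanent withdrawal of the drug, and the infusion counts in SAP 12.1 simply describe what took place.

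**Conclusion.** The inconsistency is real and worth correcting. Sections 9.4.6.3.2.1 and 9.4.6.3.2.3 give different instructions on resuming an infusion after a serious IR, 9.4.6.2 adds a rule without a seriousness limit, and nothing states which governs. The anaphylaxis element is secondary: an omitted exclusion or pointer in 9.4.6.3.2.1.

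The number of subjects affected cannot be given. The any-severity results above are ceilings. The anaphylaxis figure of about 1 in 20 assumes that a pooled post-hoc rate applies here, although transplant recipients were excluded from Phase 3, this trial applies the stopping rule prospectively, and Protocol 7.2 expects immunosuppression may lower IR risk. The sample size and the primary analysis are unchanged. The conclusion on the text rests on the wording alone and needs none of these rates.

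**What to change.** Reconcile Protocol 9.4.6.2, 9.4.6.3.2.1 and 9.4.6.3.2.3 so that a single instruction governs restarting after a serious IR and after anaphylaxis, and have 9.4.6.2 and 9.4.6.3.2.1 cross-refer to it. In the same edit, say which definition the SAE-for-IR phrase relies on, and clarify the conjunction in the last paragraph of 9.4.6.3.2.3. Which clinical rule applies is for the sponsor to decide; this review takes no position on it. The cost is protocol wording and a communication to sites. No change to the sample size or to the SAP's analyses is needed.
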